9.2.1. Statins

Use of statins (e.g., simvastatin, atorvastatin) is not allowed during the study.

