7.6. Dosage Adjustment Criteria

Dose frequency may be modified for the management of pruritus as described in [Section 14.1.3.1](#). In the event of tolerability issues such as pruritus, the dosing frequency may be decreased at the discretion of the Investigator.

Subjects can be discontinued from investigational product by the Investigator at any time for clinical safety concerns. Subjects who are discontinued from investigational product should be requested to continue with study visits until Month 60/end of study (EOS). Subjects who discontinue investigational product may be requested to come in for an Unscheduled Visit at the discretion of the Investigator depending on the timing of their next scheduled study visit.

Refer to [Section 8.4.1](#) for guidance on mandatory discontinuation of investigational product due to severe and related AEs. Refer to [Section 8.4.2](#) for other reasons of discontinuation of investigational product (e.g., withdrawal of consent, lost to follow-up, or pregnancy).

Subjects who were taking UDCA should continue this as a concomitant medication for the entirety of the study unless there is a tolerance or safety event related to UDCA that would require discontinuation.

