8.4. Subject Withdrawal Criteria

Subjects who are discontinued from investigational product should be requested to continue with study visits until Month 60/EOS. Subjects who discontinue investigational product may be requested to come in for an Unscheduled Visit at the discretion of the Investigator depending on the timing of their next scheduled study visit.

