8.4.1. Reasons for Mandatory Discontinuation of Investigational Product

Subjects will be monitored for potential hepatic decompensation events throughout the study. Clinical criteria for monitoring these events are summarized in [Table 5](#).

Investigational product will be discontinued permanently if the subject has evaluation, listing or completion, of a liver transplant or experiences other potential hepatic decompensation events as defined in Table 5. Subjects should be closely monitored until normalization or stabilization and should continue to return for scheduled study visits for safety follow-up.

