8.4.2. Other Reasons for Discontinuation of Investigational Product or Study Termination

Subjects who discontinue investigational product will be requested to continue in the study until the end of the study or at the discretion of the Sponsor; however, subjects are free to discontinue at any time.

The following events are considered appropriate reasons for a subject to be withdrawn from the study or discontinue investigational product. Subjects who discontinue investigational product are expected to continue in the study until study termination (or at the discretion of the Sponsor).

- The Investigator or Sponsor considers that it is advisable or in the best interest of the subject
- Withdrawal of consent:
 - Consent may be fully withdrawn
- Lost to follow-up
- Pregnancy
- The occurrence of clinical or laboratory AEs considered by the Investigator or Sponsor to be clinically important
- The development of any medical conditions listed in the exclusion criteria that might jeopardize patient safety ([Section 8.3](#))

The Investigator is encouraged to contact the Sponsor before discontinuing a subject from treatment. The Investigator must notify the Sponsor study monitor, also known as the Clinical Research Associate (CRA), by email as soon as possible if any subject prematurely withdraws from the study.

The Sponsor may terminate this study at any time.

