9.2. Concomitant Medications

Subjects must follow the medication restrictions outlined in the inclusion and exclusion criteria ([Section 8](#)) during the study.

Relevant information about all concomitant medications (including prescribed, over the counter, or herbal preparations) taken before (i.e., within 30 days of Day 1) and during the study must be recorded in the source documents and eCRF, as well as any dose or dose regimen changes that occur during the study. Note that on days when blood is drawn for PK sample, concomitant medications should be taken after the PK sample is taken (i.e., 6 hours post dosing).

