9.7.3. Unscheduled/Safety Visit

The Investigator may schedule an Unscheduled/Safety Visit at any time if clinically warranted based on Investigator discretion. Subjects who discontinue investigational product but continue in the study may be requested to come in for an Unscheduled Visit at the discretion of the Investigator depending on the timing of their next scheduled study visit. These subjects will then be requested to continue with regularly scheduled study visits until Month 60/EOS.

A PK sample should be collected if an unscheduled visit occurs due to a safety event. Unscheduled and/or repeat assessments, including additional laboratory tests or investigations, may be conducted at the discretion of the Investigator. As appropriate, the Medical Monitor should be contacted.

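### Protocol 9.2 and 9.2.1 bar statins, listed immunosuppressants and steroid courses over 2 weeks for the whole study, with no release for subjects who have permanently stopped the tablet but stay on visits to Month 60

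*Protocol*

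**What the plan says.** **The bar.** Protocol 9.2 opens with "Subjects must follow the medication restrictions outlined in the inclusion and exclusion criteria" and applies this during the study. Exclusion 18 in 8.3 names the drugs: statins, azathioprine, cyclosporine, methotrexate, mycophenolate mofetil and others, plus budesonide and other systemic corticosteroids, with courses of up to 2 weeks allowed. Section 9.2.1 repeats the statin ban on its own: "Use of statins (e.g., simvastatin, atorvastatin) is not allowed during the study".

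**The reason for the statin ban.** Section 9.2.8 rests it on the risk of rhabdomyolysis when bezafibrate and a statin are given together.

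**Subjects off the tablet.** Section 8.4 says "Subjects who are discontinued from investigational product should be requested to continue with study visits until Month 60/EOS", and 7.6 says the same. Section 8.4.1 adds "Investigational product will be discontinued permanently if the subject has evaluation, listing or completion, of a liver transplant" and says that these subjects "should continue to return for scheduled study visits for safety follow-up". Section 8.4.2 expects subjects who stop the tablet to remain in the study.

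**Departures.** Section 19.2 does not permit significant deviations without notifying the sponsor, unless safety calls for immediate action. SAP 9.1 treats use of prohibited medication and treatment discontinuation as intercurrent events under a treatment-policy strategy and keeps the later data.

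**The concern.** The bar is tied to being in the study, while the stated reason for its statin part is tied to taking the tablet. The two coincide during dosing and separate at permanent discontinuation. The protocol deliberately keeps those subjects under observation, for years in some cases.

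Two groups are affected. The first is the off-drug subject who comes to need a statin. That subject has also just lost a drug that 5.2 describes as approved elsewhere for hyperlipidemias. The second is the subject who has been transplanted, or who otherwise needs immunosuppression or a longer steroid course after stopping. In both, treatment with no bearing on exposure to the combination becomes a breach of 9.2. At stake are the subject's care, the number of avoidable deviations and, less certainly, retention in a study whose primary objective is long-term safety.

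**Working it through.** The documents give no figure on this point and no expected discontinuation rate, so there is nothing to reproduce. The check compares texts and adds some calendar arithmetic.

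**1. How long the bar lasts.** Sections 9.2 and 9.2.1 set it for the study. Section 7.1.4 defines a subject's study duration as at most 60 months from entry, without reference to dosing.

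**2. Whether being in the study could mean being on the tablet.** Section 9.7.3 speaks of a subject who has done one without the other: "Subjects who discontinue investigational product but continue in the study may be requested to come in for an Unscheduled Visit". The protocol therefore separates the two states.

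**3. Who can be off the tablet and still in the study.** Permanent stops follow from any Table 5 event (which include a platelet count below 150,000/µL, as well as transplant evaluation, listing or completion), a related Grade 3 adverse event (8.4.1.1), acute cholecystitis, choledocholithiasis or a gallbladder polyp over 5 mm (7.5), or a drug holiday longer than 30 days (14.1.3.1). Sections 7.6, 8.4, 8.4.1 and 14.1.3.1 keep such subjects on visits.

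**4. Whether any text releases them.** Four come near:
- 9.2.8 leaves cyclosporine to the investigator, but for use together with bezafibrate.
- 14.1.3.1 allows other therapies as clinically appropriate, but for pruritus.
- 19.2 gives a route for departures through sponsor notification. That handles a deviation; it does not remove the rule.
- 8.4.2 lets subjects leave at any time, which ends follow-up and does not lift the bar.

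None of them ends the bar at permanent discontinuation.

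**5. Whether the reason persists.** The statin reason requires bezafibrate to be present. Section 5.4.2 calls its elimination rapid, so the reason lapses after a washout, unless a CK or liver abnormality is still being followed.

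**6. Time under the bar for one subject.** For a stop at Month s (a multiple of 6, from Month 6 on), months remaining = 60 − s and scheduled visits remaining = (60 − s)/6.
- Stop at Month 6: 60 − 6 = 54 months; 54/6 = 9 visits.
- Stop at Month 30: 60 − 30 = 30 months; 30/6 = 5 visits.

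A washout of 30 days (assumed) is 30/30.4, or about 1 month, which would free 54 − 1 = 53 or 30 − 1 = 29 months. If release waits 3 months for a liver abnormality, the longest recovery of raised aminotransferases among bezafibrate subjects in the placebo-controlled trial cited in 5.4.2, it would free 54 − 3 = 51 or 30 − 3 = 27 months. These are durations of a restriction, not sizes of an effect.

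**The case against.** The best reply is that a sensible investigator would not read the rule this way. Section 9 is about treatment, 9.1.1 describes the tablet as taken for the duration of the study, and the statin reason is plainly about co-administration, so the word study may simply stand for the dosing period. That is a fair account of what the authors may have meant. It does not settle the text, because 9.7.3, in the same section, separates stopping the tablet from leaving the study, and a monitor applying 9.2 literally would record a deviation.

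Three stronger readings are tempting, and the documents do not support them.
- *An off-drug subject must go without treatment or leave.* A reader might infer this by taking 19.2 to cover urgent departures only. In 19.2 the urgent clause waives prior notification; a non-urgent need can be notified to the sponsor. Taking a prohibited drug is not among the withdrawal reasons in 8.4.2, and SAP 9.1 expects such use with data retained. Withdrawal is possible, but nothing requires it.
- *The protocol contradicts itself on immunosuppression.* Table 10 mentions oral steroid or immunosuppressive therapy in describing Grade 3 pruritus, but as part of a grading definition. The transplant remark in 9.2.8 concerns patients also taking bezafibrate. Neither addresses subjects off the tablet.
- *The cited bezafibrate trial shows how often this will happen.* Two bezafibrate subjects there received glucocorticoid, but both had histology suggestive of autoimmune hepatitis. Overlap disease is excluded here (exclusion 1), and course lengths are not given, so the 2-week limit may not have been passed. No frequency can be drawn from them.

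It also stands that entry criteria select against need. Exclusion 18 bars planned statin use, exclusion 17 covers poorly controlled dyslipidemia, and subjects with bilirubin above ULN or MELD above 12 are kept out, which makes early transplant less likely.

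**Conclusion.** The point holds as a stated rule whose reach is too wide. Read as written, the statin, immunosuppressant and longer-steroid bars continue to Month 60 for subjects who have permanently stopped the tablet and stay in follow-up. The realistic consequence is discouraged or delayed indicated care and avoidable deviations, with avoidable withdrawal only a possibility.

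The affected period can be long for one subject: 54 months after a Month 6 stop, 30 months after a Month 30 stop. The number of subjects is unknown and probably small. The conclusion assumes that sites apply 9.2 literally and that bezafibrate has cleared by the end of the washout; the 30-day figure is an example for clinical pharmacology to confirm.

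A reader might go further and infer that the efficacy estimand or the safety tables are compromised. They are not: SAP 9.1 and 9.2 already include data after prohibited medication and after discontinuation. This is a cheap improvement to subject care and conduct, not a defect in the analysis. It makes no claim about the MAOI or hepatotoxic-drug restrictions, whose liver-safety reason can outlast the tablet (14.1.9 notes that drug-induced liver injury may progress after the drug is stopped).

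**What to change.** Amend 9.2 and 9.2.1 as follows.

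1. The statin bar applies while the subject is taking the tablet, during temporary interruptions, and for a stated washout after permanent discontinuation set by clinical pharmacology (for example 30 days), and until any CK or liver abnormality being followed has returned to baseline. The protocol already uses last-dose rules of this kind for contraception (30 days for women, 90 for men).
2. Immunosuppressants and corticosteroids needed after permanent discontinuation, for example after transplant, are allowed, recorded as concomitant medication, and not counted as deviations.
3. The MAOI and potentially hepatotoxic-drug restrictions stay at least until liver tests recover.

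The same amendment could state how long the other whole-study bars last off the tablet, such as bile acid sequestrants (9.2.5); the three changes above do not reach them.

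The cost is a few sentences in the next amendment. No new visits, data collection or SAP change is needed, since 9.2 already requires concomitant medication to be recorded. The downside is somewhat more concomitant therapy in the off-drug data, which the treatment-policy approach already accepts.

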9.2.2. Monoamine Oxidase Inhibitors

Use of MAOIs (e.g., isocarboxazid, phenelzine, selegiline, and tranylcypromine) is not allowed during the study.

9.2.3. Anticoagulants

Use of anticoagulants (e.g., warfarin) should be monitored and the dose adjusted, if needed. Taken concomitantly, OCA and warfarin may decrease INR, and BZF may potentiate the action of coumarin-type anticoagulants.

9.2.4. Antidiabetics

BZF may potentiate the action of antidiabetic medications (including insulin) requiring increased monitoring of glycemic status.

9.2.5. Bile Acid Sequestrants

Subjects taking BAS (including cholestyramine and its derivatives, colestipol, colesevelam, or other BAS) or aluminum hydroxide- or smectite-containing antacids should refrain from using these drugs for the management of pruritus during the trial. The use of BAS may alter the interpretation of the effects of BZF on pruritus.

9.2.6. Estrogens

Because estrogens may lead to a rise in lipid levels, the use of BZF in patients taking estrogens or estrogen-containing contraceptives during the study must be critically considered on an individual basis and is up to the Investigators discretion.

9.2.7. Antimicrobial

Rifampin should be used with caution in patients with PBC due to the hepatotoxicity concerns as specified in the rifampin USPI.

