 5. Presence of any other disease or condition that interferes with the absorption, distribution, metabolism, or excretion of drugs including bile salt metabolism in the intestine (e.g., inflammatory bowel disease or gastric bypass procedure [gastric lap band is acceptable])
 6. Evidence or history of cholelithiasis or choledocholithiasis unless documented cholecystectomy. Gallbladder polyps if >5 mm in diameter
 7. History of chronic pancreatitis or recurrent acute pancreatitis – defined as at least 2 episodes of acute pancreatitis, with symptoms resolving between each episode
 8. History of drug-induced myopathy
 9. Chronic kidney disease (serum creatinine >1.5 mg/dL [>135 µmol/L]; CrCl <60 mL/min) or undergoing dialysis
 10. Platelet count <150,000/µL at the last visit in parent study, before transitioning to Study 977-311
 11. Known history of human immunodeficiency virus (HIV) infection
 12. History or presence of clinically concerning cardiac arrhythmias likely to affect survival during the study, QT interval of the electrocardiogram (QT) or QT interval of the electrocardiogram corrected (QTc) interval of >450 milliseconds for males and >470 milliseconds for females
 13. Severe pruritus, or required systemic treatment for pruritus (e.g., with bile acid sequestrants [BAS] or rifampicin) within 2 months of Day 1 of Study 977-311. Subjects who plan to use or will use BAS during the study will not be eligible.
 14. History of known or suspected clinically significant (CS) hypersensitivity to OCA, BZF, or other fibrates or any of their components

15. Known photoallergic or phototoxic reactions to fibrates
16. If female, known pregnancy, a positive urine pregnancy test (confirmed by a positive quantitative serum pregnancy test), or current lactation at the last visit in parent study, before transitioning to Study 977-311
17. Other CS medical conditions that are not well controlled or for which medication needs are anticipated to change during the study (e.g., Type 2 diabetes mellitus, hypothyroidism, nephritic or nephrotic syndrome, dysproteinemia, obstructive biliary disease, dyslipidemia), and/or up to the discretion of the Principal Investigator

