18. Treatment with the following medications 30 days before Day 1 of Study 977-311, or plans to use these medications during the study: azathioprine, colchicine, cyclosporine, methotrexate, mycophenolate mofetil, pentoxifylline, rifampicin, statins, budesonide and other systemic corticosteroids (short-term use up to 2 weeks is permitted), monoamine oxidase inhibitors (MAOIs), and potentially hepatotoxic drugs (including α -methyl-dopa, sodium valproic acid, isoniazid, and nitrofurantoin)
19. Treatment with the following medications within 12 months before Day 1 of Study 977-311, or plans to use these medications during the study: antibodies or immunotherapy directed against interleukins or other cytokines or chemokines
20. Participation in a study of another investigational medicine or device within 30 days before Day 1 of Study 977-311 (except for Study 747-213, Study 747-214, or other eligible Sponsor study)
21. History of or ongoing alcohol or drug abuse within 1 year before Day 1 of Study 977-311. Subjects with moderate alcohol use within 3 months prior to the last visit in parent study, before transitioning to Study 977-311, will be excluded from this study. Moderate alcohol consumption is defined as 1 standard drink per day for women and 2 drinks per day for men; whereby 1 standard drink is equivalent to: 12 oz beer (5% alcohol), 5 ounces of wine (12% alcohol), or 1.5 ounces of 80 proof (40% alcohol)
22. History of noncompliance with medical regimens, or is considered by the Principal Investigator not able to meet the requirements as specified in the protocol from Day 1 throughout the duration of the study
23. Blood or plasma donation within 30 days before Day 1
24. Mental illness or other condition which may impair decision making, such that the validity of informed consent or ability to be compliant with the study is uncertain
25. A CK value on Day 1 of Study 977-311 $\geq 5 \times$ ULN or any abnormal laboratory value that is considered CS in the opinion of the Principal Investigator and Sponsor at the last visit in parent study, before transitioning to Study 977-311
26. Known or suspected nephrotic syndrome in the last 30 days, before rolling over to this study, based on the following diagnostic criteria (both Type 1 and Type 2):
 - Proteinuria, spot urine protein: albumin/creatinine ratio (ACR) of >300 mg/mmol (subjects with normal renal function and ACR values analyzed to be below the lower limits of detection are permitted)

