14.1.3.1. Severity of Pruritus (as an Adverse Event)

To ensure consistency in reporting, pruritus AEs must be graded for severity (i.e., intensity). As pruritus is a subjective symptom, clinical judgment should be used to determine its severity and management, as shown in Table 10. In order to assess the potential improvement in pruritus with treatment, baseline pruritus presence (yes/no) and severity (as shown in Table 10) will be determined.

Table 10: Severity of Pruritus

Pruritus Grade	Clinical Description of Severity for Pruritus and Medical Intervention
1=Mild	Mild or localized; topical intervention indicated
2=Moderate	Intense or widespread; intermittent; skin changes from scratching (e.g., edema, papulation, excoriations, lichenification, oozing/crusts); oral intervention indicated; limiting instrumental activities of daily living
3=Severe	Intense or widespread; constant; limiting self-care activities of daily living or sleep; oral corticosteroid or immunosuppressive therapy indicated

Since pruritus is a subjective symptom and the occurrence and magnitude of which are not readily measured by objective tools, clinical judgment needs to be applied in the management of each subject. Managing OCA-related pruritus may help improve tolerance in those subjects who experience problematic pruritus and may otherwise discontinue from the study prematurely. General guidance for the management of subjects experiencing significant pruritus includes the following:

- Drug holiday: A drug holiday is defined as an Investigator's "prescribed" complete interruption of dosing for 1 or more consecutive days (i.e., nondaily dosing does not constitute a drug holiday). Details of drug holidays and/or nondaily dosing regimens should be recorded in the eCRF. If the drug holiday lasts more than 30 days, the subject should be permanently discontinued from investigational product but requested to continue with study visits until Month 60/EOS.
- Per [Section 8.4.1.1](#), subjects with pruritus \geq Grade 3 in severity and possibly, probably, or definitely related to the investigational product must discontinue investigational product but are encouraged to continue study visits.

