- Subjects taking BAS (including cholestyramine and its derivatives, colestipol, colesevelam, or other BAS) or aluminum hydroxide- or smectite-containing antacids should refrain from using these drugs for the management of pruritus during the trial. The use of BAS may alter the interpretation of the effects of BZF on pruritus.
- Other therapies may be tried as deemed clinically appropriate.
- Rifampin should be used with caution in patients with PBC due to the hepatotoxicity concerns as specified in the rifampin USPI.
- Less frequent dosing of investigational product (e.g., on alternate days) may be administered, after which, subjects may return to their original daily dose as soon as tolerated.

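### The protocol bars rifampicin and cyclosporine during the study, but its concomitant-medication and itch guidance reads as allowing both

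*Protocol*

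**What the plan says.** **The restriction.** Protocol 8.3, exclusion 18, excludes anyone treated in the 30 days before Day 1 with a listed drug, "or plans to use these medications during the study: azathioprine, colchicine, cyclosporine, methotrexate, mycophenolate mofetil, pentoxifylline, rifampicin, statins" among others. Section 9.2 extends this to the treatment period: "Subjects must follow the medication restrictions outlined in the inclusion and exclusion criteria" during the study. Exclusion 13 separately excludes subjects who "required systemic treatment for pruritus (e.g., with bile acid sequestrants [BAS] or rifampicin) within 2 months of Day 1".

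**The permissive text.** Section 9.2.7 consists of one sentence, beginning "Rifampin should be used with caution in patients with PBC". The on-study itch guidance in 14.1.3.1 tells subjects to refrain from bile acid sequestrants, then says "Other therapies may be tried as deemed clinically appropriate", and then gives the rifampin sentence in full: "Rifampin should be used with caution in patients with PBC due to the hepatotoxicity concerns as specified in the rifampin USPI". Section 9.2.8 notes severe myositis and rhabdomyolysis when cyclosporine is given with a fibrate, then leaves the combination to the investigator's judgement.

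**Nearby wording.** Statins and MAOIs are on the same exclusion 18 list, and Sections 9.2.1 and 9.2.2 forbid each outright during the study.

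**The concern.** A reader who combines exclusion 18 with Section 9.2 concludes that both drugs are forbidden on treatment. A reader who goes to the section on the drug, or to the guidance on managing itch, concludes that rifampin may be used with care and cyclosporine at discretion. Sites managing a symptomatic subject will more often consult the second set of sections.

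Two things are at stake. The first is subject safety: the protocol itself ties rifampin to hepatotoxicity, and cyclosporine plus a fibrate to muscle injury. The second is interpretation: SAP 10.2.4 makes hepatic injury and myalgia adverse events of special interest, and a single-arm study has no comparator to help separate the added drug from the tablet. The conflict also leaves unclear whether such use is prohibited medication under SAP 9.1, or a deviation relevant to the PK and PD populations in Protocol 15.1.

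**Working it through.** The plan gives no figure to reproduce. The check is a comparison of current protocol text, followed by one piece of arithmetic on the visit schedule.

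**Step 1. Does the ban apply after entry?** Exclusion 18 alone covers recent or planned use. Section 9.2 makes the medication restrictions binding during the study, so it does.

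**Step 2. Text side by side.** Rifampin and rifampicin are two names for one drug.

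| Drug | Exclusion 18 with 9.2 | Drug-specific text | Consistent? |
|---|---|---|---|
| Statins | barred | 9.2.1: not allowed | yes |
| MAOIs | barred | 9.2.2: not allowed | yes |
| Rifampicin | barred | 9.2.7 and 14.1.3.1: with caution | no |
| Cyclosporine | barred | 9.2.8: investigator's discretion | no |

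Conflicting sentences: rifampin 2 + cyclosporine 1 = 3. No section exempts either drug.

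**Step 3. Would a site read caution as permission?** Where Section 9.2 means a ban, it says so, as for statins and MAOIs. In 14.1.3.1 the rifampin sentence directly follows the invitation to try other therapies, and rifampin is the only named itch drug there that is not ruled out. Exclusion 13 itself names rifampicin as an itch treatment. Table 10 describes Grade 2 itch as "oral intervention indicated; limiting instrumental activities of daily living". That table grades severity and names no drug at Grade 2, so it is weak support; the order of the statements in the guidance is the stronger evidence.

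**Step 4. Who is exposed?** Exclusion 18 (30 days, or planned use) and exclusion 13 (2 months, itch treatment) screen out existing users. What remains is new, unplanned use after entry. If Grade 3 itch is "possibly, probably, or definitely related to the investigational product must discontinue investigational product". Grade 2 itch is therefore the exposed case, since the subject can stay on the tablet.

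**Step 5. How long could use run before a scheduled test?** Protocol Table 3 schedules chemistry, including CK, on Day 1, at Months 1, 3, 6 and 12, and then every 6 months to Month 60.

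- Successive gaps: 1, 2, 3 and 6 months, then 6 months each.
- Time at six-month spacing: 60 − 6 = 54 months.
- Share of the study: 54 / 60 = 90%.

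Rifampin started just after a visit in that period could run for about six months before the next scheduled liver test, unless an unscheduled visit occurs. The 90% describes the visit schedule. It is not a rate of rifampin use, which the documents do not give.

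**The case against.** The mismatch is hard to dispute; the case on the other side is that it matters little.

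- **Cyclosporine has no visible route in.** Prior liver transplantation and overlap with autoimmune hepatitis are excluded at entry, and evaluation, listing or completion of a transplant permanently stops the tablet (Protocol 7.4.3, Table 5). The text in 9.2.8 reads like background on interactions. This stands, and it makes cyclosporine secondary.
- **Monitoring is closer than the visit schedule suggests.** Under Table 4 and its footnotes, significantly worsened itch with any treatment-emergent rise in a listed liver test calls for interrupting the tablet, a search for other causes, and repeat tests 2 to 3 times per week. Section 7.4.1 asks subjects to report new medications at once, and 7.4.2 provides unscheduled tests. This narrows the gap but does not cover Grade 2 itch with normal liver tests.
- **Attribution does not rest on a comparator alone.** Hepatic and renal events are adjudicated from source documents (Protocol 14.3), and concomitant medications are recorded. This is fair: case-level review can identify the added drug. It cannot undo the exposure.
- **The sponsor may mean to treat rifampin differently from bile acid sequestrants.** That is possible, but exclusion 18 and Section 9.2 would then be wrong instead. The conflict remains either way.

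These points limit the consequence. None of the safeguards tells a site that the drug is barred.

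**Conclusion.** The concern holds. The current protocol both bars rifampicin and cyclosporine during the study and, in three sentences, reads as allowing them. Rifampin is the substantive problem, because the permissive sentence sits in the guidance for a foreseeable adverse event: Protocol 5.6.2, Table 1, gives itch as the most commonly reported event related to OCA.

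The number of subjects affected is unknown and is confined to new use after entry. The conclusion assumes that sites act on the drug-specific and itch sections as written. The six-month interval is a worst case that assumes no unscheduled test. The efficacy summaries are unaffected, because SAP 9.1 keeps data after prohibited medication under a treatment-policy strategy. This should be corrected, but it does not threaten the study's analyses.

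**What to change.** 1. In 9.2.7 and 14.1.3.1, replace the rifampin sentence with a statement that rifampin (rifampicin) is not allowed during the study, citing exclusion 18.
2. In 9.2.8, replace the cyclosporine discretion sentence with the same prohibition.
3. If the sponsor does intend to allow either drug, amend exclusion 18 instead and, for rifampicin, reconcile exclusion 13.
4. As editorial tidying in the same edit, clean up the remaining statin-combination sentences and the resin and immunosuppressant wording in 9.2.8, and the resin text in 5.6.2.

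The cost is a few sentences at the next protocol amendment, with a short memo to sites in the meantime. Data collection, the SAP and the efficacy summaries need no change.
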